5.3. Primary endpoint analysis overview

Analysis of EXPO primary outcome data will be done in two phases, as follows:

In phase I (planned data lock: quarter 3 2020), there will be a comparison of group 1 versus group 2. This comparison will include data from all 4 sites. In phase II (planned data lock: October 2021) there will be a comparison group 3 versus group 4 (data from the co-ordinating centre only).*

Following completion of the phase I and II analysis, there will be an exploratory analysis of group 1 and group 3 to compare XR-Bup and XR-Bup + PSI.

Further details of the statistical approach for these analyses is outlined in section 10 and will be specified in detail in the Statistical Analysis Plan ([SAP] to be summarised in the published protocol paper and on the Open Science Framework before data-lock).

*Due to the Coronavirus 2019 (COVID-19) pandemic and slower than anticipated recruitment rate, data lock for Phase I and Phase II will be completed at the same time; target quarter 3 2022.

6. Trial Medication

The drugs used in the trial are controlled drugs. Sites are expected to comply with the storage and supply requirements set out in the Misuse of Drugs Regulations 2001 (as amended) and the UK Controlled Drug Regulations, in addition to the trial requirements.

6.1 Investigational medicinal product

Bup extended-release injection (XR-Bup in this protocol) is licenced in the USA under the name Sublocade®. It is used for the treatment of moderate to severe OUD in patients who have initiated treatment with a transmucosal Buprenorphine product. The product is currently unlicensed in the EU. The injection is presented as a sterile, clear, viscous,

colourless to yellow amber solution in a single dose, pre-filled syringe with a 19 gauge 5/8th inch safety needle.

Bup in XR-Bup is dissolved in the ATRIGEL® delivery system. This system delivers the drug at a controlled rate over a 1-month period. The depot injection provides sustained plasma levels of Bup sufficient to block the subjective effects of exogenous opioids after a single dose and even more complete blockade after two monthly doses. The product is available in dosage strengths of 100mg/0.5ml and 300mg/1.5ml Bup. It is administered as a monthly subcutaneous injection into abdominal tissue.

Indivior will be responsible for the manufacture of the product and import into the UK. Sharp Clinical Services (UK) are contracted by Indivior to label and final Qualified Person (QP) release the product prior to distribution to investigational sites. The Simplified Investigational Medicinal Product Dossier (sIMPD), US Prescribing Information and Investigator Brochure (IB) provides further information.

6.2 Active comparators

The active comparator drugs sublingual Bup; (including sublingual Bup/Naloxone, oromucosal Bup) and oral Met will be dispensed by community pharmacies on receipt of a valid prescription, as per standard NHS practice. The drugs will be labelled with a normal dispensing label in accordance with Schedule 5 to The Medicines for Human Use (Marketing Authorisations etc) Regulations 1994. This activity is covered by Regulation 46 (2) of SI 2004/1031 of the Medicines for Human Use (Clinical Trials) Regulations (as amended).

Bup is licenced for the treatment of opioid use disorder. The tablets are available as 0.4mg, 2mg and 8mg strengths. The Summary of Product Characteristics (SmPC) for Subutex® provides further information.

Bup-NX (as hydrochloride) and naloxone (as hydrochloride dihydrate) sublingual tablets (Suboxone®) is licenced for the treatment of opioid use disorder. Suboxone® is manufactured by Indivior UK Limited. Buprenorphine is the active component of Bup/naloxone when taken sublingually. Naloxone is a deterrent to diversion and injection of the tablet and is prescribed in an identical fashion to Bup. Research sites are permitted to prescribe Bup-NX as a replacement to Bup if that is the local prescribing procedure. The tablets are available as 16mg/4mg, 8mg/2mg and 2mg/0.5mg strengths. The SmPC provides further information on this product.

Espranor® (Esp) oral lyophilisate containing (Buprenorphine as hydrochloride) and aspartame is licenced for the treatment of opioid use disorder. Buprenorphine is the active component of Esp and administration is oromucosal. Research sites are permitted to prescribe Esp as a replacement to Bup if that is the local prescribing procedure. Esp oral lyophilisate is available in 2mg/0.5mg and 8mg/2mg strengths. The SmPC provides further information on this product.

As Buprenorphine is the active component of Bup-NX and Esp they will be categorised under Bup within the protocol guidance and analysis between trial arms.

Methadone is available as a 1mg/ml solution and is licenced for the treatment of opioid use disorder. The SmPC provides further information on the product.

Participant is ineligible if they have any allergic or adverse reactions or contraindication to Buprenorphine. If participant has any allergic or adverse reaction or contraindication to Met or naloxone, or excipients of Bup-NX or Esp they can be prescribed Bup within the trial. Participants randomised to group 2 and group 4 are permitted to change between the active comparator drugs whilst enrolled in the trial by following the prescribing guidelines as detailed in the SmPC and if there are no known allergic, adverse reactions or contraindications to the drug.

6.3 Dosing regimen

Bup (active sublingual comparator): The usual dose is 8-24mg/day (Esp usual dose 8-18mg/day). Clinical practice in NHS clinics is supervised (directly observed dosing) in a community pharmacy followed by provision of patient self-administered 'take home' doses according to clinical response (i.e. informed by negative urine drug screens [UDS]; adherence to prescription; retention in treatment).

Met (active oral comparator): The recommended dose is 60-120mg/day. Clinical practice in NHS clinics is supervised (directly observed dosing) in a community pharmacy followed by provision of patient self-administered 'take home' doses according to clinical response (i.e. informed by negative UDS; adherence to prescription; retention in treatment).

In the event patients in the Met/Bup arm fail to adhere to daily dosage regime they will need to follow standard clinical protocol for that clinic.

XR-Bup (IMP active injectable comparator): The recommended dose of Sublocade® (which will be adhered to in the EXPO trial) is a 300mg loading dose, administered monthly for the first 2 months, followed by a 100mg maintenance dose for the remaining 4 months. The scheduled dosing interval is 28 days and, in EXPO, the minimum interval between the two initial loading doses is 21 days to provide increased flexibility for the participant to ensure that the loading doses are achieved. All injections will be by the site investigator, medical practitioner, nurse, or nurse practitioner who has received training in the procedure. XR-Bup is for abdominal injection into adipose tissue only (not intramuscularly). The specific area is on the abdomen between the transpyloric and trans-tubercular planes with adequate subcutaneous tissue below the waistline and above the hip bone, which is free from any lesion, mole or other skin mark.

After the two 300mg loading doses, the aim is to maintain the patient on a 100mg monthly dose if they achieve:

- no unsanctioned use of opioids
- no clinically significant opioid withdrawal
- no distressing craving for opioids and the patient is satisfied with their current dose, and requesting the dose be maintained at this level.

As a clinical guide, the maintenance dose should be increased from 100mg to 300mg under the following conditions:

- The patient is not achieving desired treatment goals (e.g. persistent unsanctioned opioid use, opioid withdrawal symptoms or distressing cravings);
- the patient does not report dose-related adverse events related to the 100mg dose (e.g. sedation or lethargy, persistent headaches, nausea);
- the patient reports that 100mg is too low and they would like a dose increase, and there are no significant clinical safety concerns.

As a clinical guide, the dose should be reduced from 300 to 100mg under the following conditions:

- The patient reports XR-Bup dose-related adverse events (e.g. sedation or lethargy, persistent headaches, nausea);
- the patient is seeking to reduce their dose in an attempt to ultimately withdraw from opioid agonist treatment;
- the patient reports that 300mg is 'too high' and they would like a dose decrease, and there are no significant concerns regarding deterioration in clinical condition (e.g. substance use, physical or mental health symptoms) that may arise with a dose reduction.)

On the basis of patient report and clinical judgement of the risks and benefits, rescue dosing of Bup can be provided at any point after the first dose of XR-Bup. This will be recorded as concomitant medication.

Whilst maintenance doses will be routinely scheduled to occur every 28 days, flexibility was included in the development research for Sublocade® and this will be followed in the EXPO trial to accommodate patients who need to attend other appointments or have travel problems attending the clinic.

In summary, the protocol allows for:

- (1) the second 300mg loading dose of XR-Bup to be given after a minimum of 21 days;
- (2) each planned 100mg maintenance doses can be administered up to 2 days ahead of the scheduled dose (i.e. 26 days since the last injection); and
- (3) all subsequent doses after the first dose to be given up to 14 days after the 28-day scheduled dose (i.e. to 42 days).

Unexpected delays of up to 14 days are not anticipated to have any clinical impact on treatment response given the reported extended-release profile of the IMP.

Following the 6th dose, there is an optional consent for participants who are randomised to XR-Bup to continue receiving doses every 28 days until the date that the last participant is randomised within the EXPO Trial plus 9 months.

In summary, the dosing schedule for EXPO is shown below:

Dose	Day	Visit	Window	XR-BUP dose
1	1	Baseline	-	300mg
2	28	Week 4	21-42	300mg
3	56	Week 8	54-70	100mg or 300mg
4	84	Week 12	82-98	100mg or 300mg
5	112	Week 16	110-126	100mg or 300mg
6	140	Week 20	138-168	100mg or 300mg
7 onwards	168 onwards	Week 24 onwards (every 28 days)	Up to 42 days since previous dose	100mg or 300mg

If the participant misses a scheduled maintenance of XR-Bup no adjustment in dose is required, if they receive this dose within 60 days of their last injection. If the participant does not receive an XR-Bup dose within 60 days of their last injection, the participant is not withdrawn from study treatment; but a clinical assessment by the principal investigator (PI) is needed to determine if there has been any illicit opioid use and the optimal starting dose.

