IMP, dosage and route of administration	
Buprenorphine extended-release depot injection (USA Sublocade®; XR-Bup) is administered by subcutaneous injection into abdominal tissue. XR-Bup is available as a 100mg/0.5ml and 300mg/1.5ml pre-filled syringe. In EXPO, the drug is administered as two initial doses of 300mg given a minimum of 21 days apart, followed by 4 x 100 mg monthly maintenance doses.
 
Within the regimen and if the benefits are judged to outweigh the risks: (1) The 100 mg maintenance dose may be increased and maintained to 300mg if there is unsatisfactory clinical response (i.e. dose 3-6); (2) A 300 mg maintenance dose (i.e. dose 4 and 5) may be reduced to 100 mg according to clinical assessment; (3) Bup will be given on a rescue

	basis for patients who do not achieve a satisfactory clinical response to XR-Bup.
Active comparator product(s)	(1) Bup (sublingual [tablet] Bup, or substitute 4:1 ratio Bup/naloxone 'Suboxone' [Bup- NX]) usual dose 12-24mg/day; or substitute oral lyophilisate Espranor (Esp) usual dose 8-18mg/day) are longstanding standard-of-care maintenance pharmacotherapy for OUD in the NHS. (2) Met (oral methadone hydrochloride; usual dose 60-120mg/d), longstanding standard-of-care maintenance pharmacotherapy for OUD in the NHS.
Maximum duration of treatment for participant	40 months
Electronic CRF	InferMED MACRO (programmed by King's Clinical Trials Unit [KCTU])
Clinical trials unit	KCTU (on-line randomisation)
Study Phases	Data lock 1: target quarter 3, 2022 for analysis of XR-Bup vs. Bup/Met. Data lock 2: target quarter 3, 2022 for analysis of XR-Bup + PSI vs. Bup/Met + PSI.
Target duration of study	48 months
Protocol Amendments	Detailed in Section 25 of the protocol

2. Study Contacts

[name] (Chief Investigator [CI] and Principal Investigator) Clinical Lead Lambeth Addictions SLaM Drug and Alcohol Service (Lambeth) [name] [name] w: [name]; m: [name] email: [contact]
	
[name] (Co-Lead Investigator [Co-LI]) Research Lead Lambeth Addictions Institute of Psychiatry, Psychology & Neuroscience Box 48, Addiction Sciences Building [name] w: [name]; m: [name] f: [name]; email: [contact]

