8.3 Selection of participants

All participants for EXPO will be recruited from specialist NHS addictions treatment programmes in community settings and already in receipt of opioid substitution therapy. Patients will consent prior to any screening procedures and will be randomised at a minimum of 24 hours post consent.

Post- randomisation treatment is summarised as follows:

Participants randomised to standard-of-care oral maintenance

Participants who are allocated to oral opioid pharmacotherapy will receive Bup/Met according to medical screening and informed by patient preference, following each site's usual screening, induction/stabilisation and maintenance dosing and medication dispensing procedure. There will be an additional requirement to attend the clinic after 2 weeks and then at least monthly to complete research measures and a urine drug screen procedure.

Met participants randomised to XR- Bup

Met participants will firstly be converted to Bup by following the sites local clinical procedure. Once stabilised on Bup, participants will require a period of at least 3 days on 8mg-24mg of Bup before they can receive the first dose of XR- Bup. The last dose of Bup is to be taken 1 day prior to the first dose of XR- Bup. Participants should receive their first injection of XR-Bup within 7 days of randomisation.

Bup participants randomised to XR- Bup

If the participant is prescribed less than 8mg of Bup there will be a minimum 3-day lead-in on 8mg Bup prior the first dose of XR-Bup. Participants who were previously prescribed 8mg or higher BUP can receive XR-Bup upon agreement of a suitable time with the participant and EXPO research team. The last dose of Bup is to be taken 1 day prior to the first dose of XR- Bup. Participants should receive their first injection of XR-Bup within 7 days of randomisation.

For all participants if during the transition period, the participant decides not to receive XR- Bup or clinical judgement deems it unsuitable to continue the participant will be withdrawn from the trial (ITT population).

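### Protocol 6.3 times XR-Bup doses from the last injection in its rules but by fixed study days in its table, and the two do not agree

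*Protocol*

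**What the plan says.** All of this is in Protocol 6.3 unless noted.

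**Rules counted from the previous injection.** "The scheduled dosing interval is 28 days". Rule (1) allows "the second 300mg loading dose of XR-Bup to be given after a minimum of 21 days". Rule (2) says "each planned 100mg maintenance doses can be administered up to 2 days ahead of the scheduled dose (i.e. 26 days since the last injection". Rule (3) allows "all subsequent doses after the first dose to be given up to 14 days after the 28-day scheduled dose (i.e. to 42 days".

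**Table counted in study days.** The summary table at the end of the section gives a nominal day and a window for each dose, for example "Week 16 110-126" for dose 5. The full set is:
- dose 1: day 1, visit labelled Baseline, no window
- dose 2: day 28, window 21-42
- dose 3: day 56, window 54-70
- dose 4: day 84, window 82-98
- dose 5: day 112, window 110-126
- dose 6: day 140, window 138-168
- dose 7 onwards: from day 168, every 28 days, with the window "Up to 42 days since previous dose"

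**Missed doses.** A missed maintenance dose needs no dose adjustment if it is given within 60 days of the last injection.

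**First injection.** Section 8.3 says "Participants should receive their first injection of XR-Bup within 7 days of randomisation".

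**Dose reduction.** The synopsis, repeated in SAP 3.1, says "A 300 mg maintenance dose (i.e. dose 4 and 5) may be reduced to 100 mg according to clinical assessment". The guide to dose reduction in 6.3 names no dose numbers.

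**The concern.** The rules and the table measure different things. A window tied to days since the last injection moves with each patient's dosing dates; a window tied to the study day does not. Once one dose is given early or late, the two can give different answers for the next dose, and the protocol does not say which governs.

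This is the schedule for the investigational depot product at five sites. A site working from the table alone can give two injections closer together, or further apart, than the stated interval. The protocol's own reassurance about late dosing covers delays of up to 14 days, that is, to 42 days since the last injection, and it offers none for intervals below 26 days. There is also a reporting consequence. SAP 4.4 promises a description of injection frequency and dosing pattern, and SAP 4.5 monitors deviations. Neither gives a timing rule for injections after the first, so whether an injection was on schedule depends on which part of 6.3 is read.

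**Working it through.** **1. The stated interval.** From the 28-day schedule: earliest 28 − 2 = 26 days, latest 28 + 14 = 42 days. Both figures in the text reproduce. The 26-day limit is worded for planned 100mg maintenance doses; the 42-day limit covers all doses after the first.

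**2. How the table was built.** Applying −2/+14 to the nominal study day (−7/+14 for dose 2):

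| Dose | Nominal day | Pattern gives | Table gives |
|---|---|---|---|
| 2 | 28 | 21-42 | 21-42 |
| 3 | 56 | 54-70 | 54-70 |
| 4 | 84 | 82-98 | 82-98 |
| 5 | 112 | 110-126 | 110-126 |
| 6 | 140 | 138-154 | 138-168 |

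Doses 2 to 5 apply the allowances to the study day, not to the last injection. Dose 6 ends 168 − 140 = 28 days after its nominal day.

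**3. Gaps that the table alone permits.** Minimum = lower limit of the next window − upper limit of the previous one. Maximum = upper limit of the next − lower limit of the previous.

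| Doses | Minimum (days) | Maximum (days) |
|---|---|---|
| 2-3 | 54 − 42 = 12 | 70 − 21 = 49 |
| 3-4 | 82 − 70 = 12 | 98 − 54 = 44 |
| 4-5 | 110 − 98 = 12 | 126 − 82 = 44 |
| 5-6 | 138 − 126 = 12 | 168 − 110 = 58 |

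Every pair can fall below 26 and above 42 days while each dose is inside its window.

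**4. The other direction.** Latest day by the 42-day rule after the latest in-window previous dose, against the table limit:
- dose 3: 42 + 42 = 84, table closes at 70
- dose 4: 70 + 42 = 112, table closes at 98
- dose 5: 98 + 42 = 140, table closes at 126
- dose 6: 126 + 42 = 168, table closes at 168

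So the table is also stricter than the text for doses 3 to 5. Only for dose 6 do the two upper limits coincide, which suggests that this row may have been built on the interval basis and the others on the study-day basis. The protocol does not say so. Day 168 is also the day dose 7 opens.

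**5. Can both limits be met?** A dose on day *a* leaves a date satisfying both if *a* + 26 is no later than the next window's end and *a* + 42 is no earlier than its start. It is enough to test the last and first day of each window:
- doses 2-3: 42 + 26 = 68 ≤ 70; 21 + 42 = 63 ≥ 54
- doses 3-4: 70 + 26 = 96 ≤ 98; 54 + 42 = 96 ≥ 82
- doses 4-5: 98 + 26 = 124 ≤ 126; 82 + 42 = 124 ≥ 110
- doses 5-6: 126 + 26 = 152 ≤ 168; 110 + 42 = 152 ≥ 138

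Yes, from every date in windows 2 to 5. The room can be small: after dose 2 on day 42, only days 68 to 70 satisfy both.

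**6. How much is due to dose 6?** If that row had followed the pattern in step 2 (an illustration, not a proposal), the 5-6 maximum would be 154 − 110 = 44. The 12-day minima would not change. The dose 6 row explains only part of the spread.

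**7. Day origin.** If Day 1 is the day of the first injection, day 21 is 21 − 1 = 20 days later, against the stated 21-day minimum. If Day 1 is baseline or randomisation, the first injection may fall up to 7 days after randomisation and the table does not say whether later windows shift with it.

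**8. The 60-day provision.** All the table maxima (49, 44, 44, 58) lie below 60 days.

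**The case against.** The best defence is that the rules and the table stand next to each other and are meant to be read together. Nothing says that the table replaces the rules, and step 5 shows that a site observing both can always comply. That stands: the table permits a breach of the stated interval but does not force one. What the defence lacks is a sentence saying that both limits apply.

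The 60-day provision is a second defence, since every long gap falls inside it. But it concerns dose adjustment after a missed dose and does not restate the scheduling limit. It says nothing about short gaps.

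Four stronger readings are tempting and are not supported:
- **A zero-day gap between doses 6 and 7.** Dose 6 may be given to day 168 and dose 7 opens on day 168, but the dose 7 row itself specifies dosing every 28 days. What remains is that its Window column gives only an upper limit.
- **Loading doses 14 days apart.** Counting from randomisation, injections on days 7 and 21 would both fit the table, but 6.3 expressly sets a 21-day minimum between the two loading doses.
- **Dose 6 at day 168 as a breach of the 42-day rule.** Counted from the latest dose 5 (day 126) it is exactly 42 days. It departs from the table's pattern without always breaking the rule.
- **Mistimed injections passing with no deviation recorded.** No text says that deviations are judged by the table alone, and neither the eCRF checks nor the Investigational Product Handling Manual is among the documents.

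On dose reduction, dose 3 at 100mg is the planned step down from loading, so within the six-dose course the mismatch between the synopsis and 6.3 comes down mainly to dose 6.

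**Conclusion.** The point holds as an unreconciled conflict within Protocol 6.3. The rules give 26 to 42 days since the last injection; the table read alone gives 12 to 49 days (doses 2-3), 12 to 44 (3-4 and 4-5) and 12 to 58 (5-6), and for doses 3 to 5 it can also close up to 14 days before the 42-day rule does. These are extremes of what is permitted, not forecasts of practice. They assume a site that follows the table without the rules, and they treat the 26-day minimum as applying to doses 3 to 6. That minimum is worded for planned 100mg doses, so for a 300mg maintenance dose no minimum is expressly stated.

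The dose 6 upper limit, the missing lower limit for dose 7 and the day origin are parts of the same problem. The synopsis wording on dose reduction is a smaller, separate inconsistency. Because these are instructions for giving the investigational product, they need reconciling even though compliance with both is possible. Sample size and power are unaffected, and the primary analysis is by intention to treat. Any effect on the per-protocol sensitivity analyses is not established, because SAP 6.9 does not list injection timing after the first dose among its examples.

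**What to change.** The sponsor and investigators should reconcile interval rules (1) to (3), the dosing table including the dose 6 and dose 7 rows, the 60-day missed-dose provision and the synopsis wording on dose reduction, which SAP 3.1 repeats. The reconciled text should state:
- one basis for the windows (study day or days since last injection), or that both limits must be met
- one day origin, saying whether Day 1 is randomisation, baseline or the first injection
- whether the minimum interval for planned 100mg maintenance doses also covers 300mg maintenance doses and doses from the seventh onwards

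Any eCRF window check, and the description of adherence in the SAP, should use the same rule. Which interval or dose rule is right is for the sponsor and investigators. The cost is a protocol clarification and, if needed, an edit check in the eCRF.
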